6.2.2. Week 48 Assessments – End of Blinded Randomized Treatment

Study Visit for Week 48 should be completed ± 4 days of the protocol-specified visit date, based on the Baseline Visit. The following assessments and procedures will be performed and recorded on CRFs:

- Complete physical examination including Tanner Staging and vital signs
- Body weight and height
- Blood samples for:
 - Hematology (CBC with differential and platelet count)
 - Serum chemistry and liver function tests, including albumin, alkaline phosphatase, AST, ALT, total bilirubin (reflex to direct [conjugated] bilirubin if total bilirubin $> 1.5 \times$ ULN), bicarbonate, BUN, calcium, chloride, CPK, creatinine (and calculated creatinine clearance), glucose, LDH, magnesium, phosphorus, potassium, sodium, uric acid, and amylase (reflex lipase testing if total amylase is $\geq 1.5 \times$ ULN)
 - Serum bone biochemical markers, including serum c-telopeptides, osteocalcin, bone-specific alkaline phosphatase, PTH, vitamin D levels (25-hydroxy), 1,25 (dihydroxyvitamin) D levels, and fasting creatinine and fasting phosphate
 - Hepatitis B serology (HBeAg and HBsAg; reflex HBeAb and HBsAb if Ag negative)
 - Plasma HBV DNA (PCR method)
 - Serum β -HCG pregnancy test (females of childbearing potential only)
 - Serum for resistance surveillance
 - Plasma for determination of tenofovir concentration
 - Serum and plasma for storage (for potential pharmacokinetic and/or virologic assays, including resistance surveillance, HBsAg and HBeAg quantification and compliance assessment)

- Urine samples for:
 - Urinalysis (protein, glucose, blood)
 - Urine bone biochemical markers, including urine bicarbonate, urine n-telopeptide, and spot urine creatinine and phosphate
- DEXA scan of spine and whole body (DEXA scans may be performed \pm 10 days from the Week 48 visit).
- Review of AEs and concomitant medications
- Retrieval of study medication and assessment of medication adherence
- Study drug dispensing (including multivitamin) and instructions on appropriate dosing and administration

After 48 weeks of blinded randomized treatment, each subject will switch to open-label tenofovir DF treatment for an additional 144 weeks. Subjects under Protocol Amendment 3 who are beyond Week 48 of blinded randomized treatment will switch to open-label tenofovir DF at the Week 72 visit and will continue on open-label treatment until Week 192.

Subjects who discontinue the study prior to the Week 48 Visit will complete an Early Study Drug Discontinuation Visit as detailed in Section 6.3. Subsequent off-study therapy, if any, is at the discretion of the subject/physician and will not be provided by Gilead Sciences. Subjects who have received at least one dose of study drug and permanently discontinue study drug will be followed for 24 weeks off treatment or up to initiation of active treatment, whichever occurs first.

6.2.3. Assessments for Weeks 56, 64, 72, 80, 88, 96, 108, 120, 132, 144, 156, 168, 180, and Extension Phase

After Week 48 through the end of the study treatment (Week 192), subjects will return for visits at Weeks 56, 64, 72, 80, 88, 96, 108, 120, 132, 144, 156, 168, and 180. Each study visit will occur \pm 6 days from the protocol-specified visit date, based on the Baseline Visit.

Subjects in this study who complete all study visits and are on tenofovir DF at the Week 192 visit will be eligible to continue in the Extension Phase of the study, where they will receive open-label tenofovir DF (dose adjusted for weight) until Viread is commercially available in that country for treatment of Chronic HBV in patients of their age and weight. During the Extension Phase, subjects will return for visits every 12 weeks to assess efficacy and safety, to conduct study drug accountability, and dispense study drug. Study Visits for the Extension Phase should be completed within \pm 14 days of the protocol-specified visit date, based on the Baseline Visit. When commercial Viread becomes available, subjects will complete the End of Treatment Visit assessments at the next scheduled visit (see Section 6.2.4), and the subject's participation in the study will end.

The following assessments and procedures will be performed during these visits and recorded on CRFs:

- Symptom-directed physical examination, including vital signs (complete physical examination including Tanner Staging at Weeks 72, 96, 120, 144, 168, and every 48 weeks during Extension Phase)
- Body weight and height
- Blood samples for:
 - Hematology (CBC with differential and platelet count)
 - Serum chemistry and liver function tests, including albumin, alkaline phosphatase, AST, ALT, total bilirubin (reflex to direct [conjugated] bilirubin if total bilirubin $> 1.5 \times$ ULN), bicarbonate, BUN, calcium, chloride, CPK, creatinine (and calculated creatinine clearance), glucose, LDH, magnesium, phosphorus, potassium, sodium, uric acid, and amylase (reflex lipase testing if total amylase is $\geq 1.5 \times$ ULN)
 - At Weeks 96, 144, and every 48 weeks during the Extension Phase: Serum bone biochemical markers, including serum c-telopeptides, osteocalcin, bone-specific alkaline phosphatase, PTH, vitamin D levels (25-hydroxy), 1,25 (dihydroxyvitamin) D levels, and fasting creatinine and fasting phosphate
 - Hepatitis B serology (HBeAg and HBsAg; reflex HBeAb and HBsAb if Ag negative) (Weeks 64, 72, 80, 96, and then every 12 weeks until the end of the study including the Extension Phase)
 - Plasma HBV DNA (PCR method)
 - Plasma for determination of tenofovir concentration
 - At Weeks 96 and 144: Serum for resistance surveillance
 - Serum and plasma for storage (for potential pharmacokinetic and/or virologic assays, including resistance surveillance, HBsAg and HBeAg quantification and compliance assessment)
- Urine samples for:
 - Urinalysis (protein, glucose, blood)
 - Urine pregnancy test (for females of childbearing potential only; positive urine pregnancy test will be immediately confirmed with a serum pregnancy test)
 - At Weeks 72, 96, 144, and every 48 weeks during the Extension Phase: Urine bone biomarkers, including urine bicarbonate, urine n-telopeptide, and spot urine creatinine and phosphate

- Weeks 72, 96, 144, and every 48 weeks during the Extension Phase: DEXA scan of spine and whole body (DEXA scan must be performed \pm 10 days from scheduled study visit)
- Review of AEs and concomitant medications
- Retrieval of study medication and assessment of medication adherence
- Study drug dispensing (including multivitamin) and instructions on appropriate dosing and administration
- At Week 56 only: Provide all subjects with a Subject Dosing Diary Card to complete the diary for 10 days prior to the next visit.
- At Week 64 only: Collect the Subject Dosing Diary Card completed by the subject daily for 10 days prior to these visits.

6.2.4. Week 192 Assessments/Early Discontinuation/End of Treatment

Study Visit for Week 192 should be completed \pm 6 days of the protocol-specified visit date, based on the Baseline Visit. If the Early Discontinuation visit is performed prior to Week 96, DEXA and bone biochemical markers are required if the previous measurements were $>$ 12 weeks prior. If the Visit is performed after Week 96 or after the Extension Phase, DEXA and biochemical markers are required if the previous measurements were $>$ 24 weeks prior.

The following assessments and procedures will be performed and recorded on CRFs:

- Complete physical examination including Tanner Staging and vital signs
- Body weight and height
- Blood samples for:
 - Hematology (CBC with differential and platelet count)
 - Serum chemistry and liver function tests, including albumin, alkaline phosphatase, AST, ALT, total bilirubin (reflex to direct [conjugated] bilirubin if total bilirubin $>$ $1.5 \times$ ULN), bicarbonate, BUN, calcium, chloride, CPK, creatinine (and calculated creatinine clearance), glucose, LDH, magnesium, phosphorus, potassium, sodium, uric acid, and amylase (reflex lipase testing if total amylase is $\geq 1.5 \times$ ULN)
 - Serum bone biochemical markers, including serum c-telopeptides, osteocalcin, bone-specific alkaline phosphatase, PTH, vitamin D levels (25-hydroxy), 1,25 (dihydroxyvitamin) D levels, and fasting creatinine and fasting phosphate
 - Hepatitis B serology (HBeAg and HBsAg; reflex HBeAb and HBsAb if Ag negative)

- Plasma HBV DNA (PCR method)
- Serum β -HCG pregnancy test (females of childbearing potential only)
- Serum for resistance surveillance
- Plasma for determination of tenofovir concentration
- Serum and plasma for storage (for potential pharmacokinetic and/or virologic assays, including resistance surveillance, HBsAg and HBeAg quantification and compliance assessment)
- Urine samples for:
 - Urinalysis (protein, glucose, blood)
 - Urine bone biochemical markers, including urine bicarbonate, urine n-telopeptide, and spot urine creatinine and phosphate
- DEXA scan of spine and whole body (DEXA scans may be performed \pm 10 days from the Week 192 visit). Review of AEs and concomitant medications
- Retrieval of study medication and assessment of medication adherence

Subjects who discontinue the study prior to the Week 192 Visit will complete all Week 192 assessments and procedures at an Early Study Drug Discontinuation Visit, to be completed within 72 hours of last dose of study drug. Subsequent off-study therapy, if any, is at the discretion of the subject/physician and will not be provided by Gilead Sciences. Subjects who have received at least one dose of study drug and permanently discontinue study drug will be followed for 24 weeks off treatment or up to initiation of active treatment, whichever occurs first.

The study treatment will end after the each subject reaches Week 192. At Week 192, all active subjects will be offered tenofovir DF through the Extension Phase of the protocol until it becomes commercially available in that country for treatment of chronic HBV in patients of their age and weight. If the subject is off treatment following Week 192, the treatment-free follow-up period is required (Section 6.3.1).

6.3. Post-Treatment/Treatment-Free Follow-up Assessments

6.3.1. Follow-Up Assessments

For subjects with known bridging fibrosis or cirrhosis, study drug discontinuation with treatment-free follow-up is contraindicated due to the potential risk of exacerbation of hepatitis in the setting of low hepatic reserve which could lead to decompensation. Subjects with bridging fibrosis or cirrhosis should be placed on commercially available HBV therapy following study drug discontinuation.

Subjects who have received at least one dose of study drug and permanently discontinue study drug will be followed for 24 weeks off treatment or up to initiation of active treatment, whichever occurs first. The treatment-free follow-up period could occur for early discontinuation subjects or at Week 192 study completion.

For those subjects who remain off treatment, the following evaluations are to be completed every 4 weeks through the Week 24 Follow-Up Visit (Follow-Up Weeks 4, 8, 12, 16, 20 and 24). Each follow up visit should be conducted within ± 3 days from the protocol-specified visit date, calculated from the date of last dose.

- Symptom-directed physical examination, including vital signs
- Body weight and height
- Blood samples for:
 - Serum chemistry and liver function tests, including albumin, alkaline phosphatase, AST, ALT, total bilirubin (reflex to direct [conjugated] bilirubin if total bilirubin $> 1.5 \times$ ULN), bicarbonate, BUN, calcium, chloride, CPK, creatinine (and calculated creatinine clearance), glucose, LDH, magnesium, phosphorus, potassium, sodium, uric acid, and amylase (reflex lipase testing if total amylase is $\geq 1.5 \times$ ULN)
 - Hepatitis B serology (HBeAg and HBsAg; reflex HBeAb and HBsAb if Ag negative) (Follow-Up Week 24 only)
 - Plasma HBV DNA (PCR method)
 - Serum and plasma for storage (for potential pharmacokinetic and/or virologic assays, including resistance surveillance, HBsAg and HBeAg quantification and compliance assessment)
 - Prothrombin time (PT), international normalized ratio (INR) (reflex test in case of post-treatment exacerbation of hepatitis)
- Review of AEs and concomitant medications

Subjects experiencing post-treatment exacerbation of hepatitis during the 24-week post-treatment period should be followed weekly until their ALT levels return to Grade 2 or baseline, as described in the Toxicity Management section of the protocol (Section 7.6.)

6.3.2. Assessments for Premature Discontinuation from the Study (Early Study Drug Discontinuation Visit)

Subjects who permanently discontinue study drug prior to the end of the study (Week 192) will be asked to return to the clinic within 72 hours of stopping study drug for an Early Study Drug Discontinuation Visit. Subjects who discontinue the study prior to the Week 192 Visit will complete all Early Discontinuation assessments and procedures (see Section 6.3.1 above). Subjects who have received at least one dose of study drug and permanently discontinue study drug will be followed with visits every 4 weeks for 24 weeks off treatment or up to initiation of active treatment, whichever occurs first. Subsequent off-study therapy, if any, is at the discretion of the subject/physician and will not be provided by Gilead Sciences.

Subjects experiencing post-treatment exacerbation of hepatitis during the 24-week post-treatment period should be followed weekly until their ALT levels return to Grade 2 or baseline, as described in the Toxicity Management section of the protocol (Section 7.6).

6.4. Bone Mineral Density

Dual energy x-ray absorptiometry (DEXA) scans will be performed between the Screening and the Baseline Visits, at Weeks 24, 48, 72, 96, 144, 192, every 48 weeks during the Extension Phase, and the Early Study Drug Discontinuation/End of Treatment Visit, if applicable, using pediatric software approved by the DEXA vendor selected by Gilead Sciences. **Randomization may not occur until after the Baseline (pre-treatment) DEXA scan has been performed.** Subsequent DEXA scans should be performed within 10 days of the scheduled visit. In addition, a DEXA scan will be performed at the time of switch in subjects switching from placebo to tenofovir DF, unless the previous scan was ≤ 12 weeks earlier. Scans will be made of the spine and whole body to measure changes in bone mineral density and bone mineral content. All DEXA scan results (spine bone mineral density, whole body bone mineral density) will be provided to the study sites.

A complete description of the procedures to be performed for the DEXA scans will be provided by the DEXA vendor in a DEXA procedure manual.

6.5. Bone Biochemical Markers

Laboratory samples will be taken at screening, baseline and at Weeks 24, 48, 72, 96, 144, 192, every 48 weeks during the Extension Phase, and the Early Study Drug Discontinuation/End of Treatment Visit, if applicable, for measuring bone biochemical markers. In addition, bone biochemical markers will be measured at the time of switch in subjects switching from placebo to tenofovir DF, unless the previous measurements were ≤ 12 weeks prior.

Analyses will include measurements of urine bicarbonate and n-telopeptide; measurements of serum c-telopeptides, osteocalcin, bone-specific alkaline phosphatase, PTH, and vitamin D levels (25-hydroxy) and 1,25 (dihydroxyvitamin) D levels; and fasting serum creatinine/phosphate and urine creatinine (spot)/phosphate for measurement of the renal phosphate threshold (TmP/GFR).

The mean of the Screening and Baseline Visit values will constitute the study baseline value to which all subsequent values will be compared. Bone biochemical markers can be affected by the time of day (diurnal variation) and food. Therefore, subjects will be asked to report for each of these visits in the morning in a fasted state or, if fasting is not feasible, at the same time (± 2 hours from the Baseline Visit draw time) at each subsequent visit. All samples will be sent to a central laboratory in accordance with the laboratory procedure manual. Bone biochemical marker results will not be provided to the study sites.

6.6. Pharmacokinetic Assessment

Two intensive PK substudies will be performed on a subset of subjects in two separate cohorts; an oral powder and a tablet cohort. Each cohort will have an intensive PK substudy performed over one day between Week 2 and Week 12 to evaluate the PK of different tenofovir DF formulations in a pediatric population.

Powder Cohort

Subjects who are eligible to take the oral powder (either tenofovir DF or matching placebo) based on body weight and/or preference for this dosage form, and subjects who qualify for the tablet formulation but are willing to initiate treatment with the oral powder for purposes of accruing additional PK data, will be offered the opportunity to participate in the oral powder cohort. Up to 30 randomized subjects will be able to participate in the powder cohort. In order to participate in the oral powder cohort, the subject must be taking the oral powder for at least 2 weeks prior to the intensive PK visit.

Tablet Cohort

Randomized subjects who are assigned to take tablet (either tenofovir DF or matching placebo) will be offered the opportunity to participate in the tablet cohort. A target of 12 subjects will be enrolled in the tablet cohort at each dosage level (150, 200, 250, 300 mg). Subjects may participate in both the powder and the tablet cohorts intensive PK substudies, with the second intensive PK substudy occurring after the Week 12, but prior to the end of the double-blind phase. For those subjects who opt to initiate treatment with oral powder and subsequently switch to tablets following completion of the powder intensive PK visit, or those subjects who are required to change dose strengths of the tablet based on the weight-based dosing requirement (see protocol Section 5.3) will also have the option to participate in a second tablet intensive PK visit. Subjects initially treated with tablets or subjects switching from oral powder to tablet, must be receiving tablets for at least two weeks prior to the tablet intensive PK visit.

Intensive and Sparse PK Sampling

Both cohorts (oral powder and tablets) will have the intense PK sampling occurring over a single day for a period of 8 hours. Specimens will be drawn at 0 hours (pre-dose), and at 1, 2, 4, and 8 hours after study drug dosing (tenofovir DF or placebo).

Additionally, sparse PK sampling will be performed on all subjects at every study visit to monitor for adherence and potentially for other PK analyses (e.g. population pharmacokinetics). At the time each blood sample is collected (both intensive and sparse sampling), the following information will be recorded:

- The date and time of last dose taken
- Whether last dose was taken with or without food
- The date and time of blood draw

All specimens will be sent to an external lab for analysis. Details of the substudy procedures and specimen management will be described in the PK manual.

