Subjects who are eligible to take the oral powder (either tenofovir DF or matching placebo) based on body weight and/or preference for this dosage form, and subjects who qualify for the tablet formulation but are willing to initiate treatment with the oral powder for purposes of accruing additional PK data, will be offered the opportunity to participate in the oral powder cohort. Those subjects who opt to initiate treatment with oral powder and subsequently switch to tablets following completion of the powder intensive PK visit, or those subjects who are required to change dose strengths of the tablet based on the weight-based dosing requirements (see protocol Section 5.3) will also have the option to participate in a second tablet intensive PK visit.

Irrespective of choice of formulation (tablet versus oral powder), if a subject is switching from tablets to powder, the subject must be taking powder for at least 2 weeks prior to the powder intensive PK visit. Similarly, subjects must be taking tablets for at least 2 weeks prior to the tablet intensive PK visit.

Statistical Methods:

The primary efficacy analysis will be conducted at the end of double-blind treatment, after the last randomized subject reaches Week 48. The analysis will evaluate the difference in the proportion of subjects achieving the primary efficacy endpoint between the tenofovir DF and placebo treatment groups using a two-sided Fisher's exact test with missing data handled using a missing = failure approach. Efficacy analyses of all subjects continuing on open-label tenofovir DF will be performed after the last randomized subject reaches Weeks 144 and 192.

Subgroup analyses of efficacy endpoints may include analyses by randomization stratification group (age [2 to < 6 and 6 to < 12] and geographical location of study site [North America/Europe and Asia]).

The proportion of subjects in each treatment arm with an adverse event or an abnormal laboratory test will be summarized at Week 48 and also at Weeks 144 and 192.

All continuous endpoints will be summarized using n, mean, standard deviation, median, Q1, Q3, minimum and maximum by treatment group. All categorical secondary endpoints will be summarized by number and percentage of subjects who meet the endpoint.

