Plasma and serum for storage will be collected at every visit starting at Baseline for possible PK and/or virological analyses (including resistance surveillance, HBsAg and HBeAg quantification, and adherence assessment).

For subjects in whom a separate consent is provided, a blood sample for biomarker analysis (including pharmacogenomic analysis) will be collected for the exploration of appropriate markers that may be predictive of virologic response and/or the tolerability of HBV therapies.

Intensive PK Substudy

To evaluate the PK of different formulations of TDF in the pediatric population, 2 intensive PK substudies (oral powder and tablet cohorts) will be performed on a subset of subjects. The intensive PK sampling will be performed over 8 hours during one day between Week 2 and Week 12.

A target of 12 randomized subjects at each dosage level (150, 200, 250, and 300 mg) will be enrolled in the tablet cohort, and up to a total of 30 randomized subjects will be enrolled in the oral powder cohort.

Subjects are allowed to participate in up to 2 intensive PK substudies with the second intensive PK substudy occurring after Week 12 but prior to the end of the double-blind phase.

Subjects who are eligible to take the oral powder (either TDF or matching placebo) based on body weight and/or preference for this dosage form, and subjects who qualify for the tablet formulation but are willing to initiate treatment with the oral powder for purposes of accruing additional PK data, will be offered the opportunity to participate in the oral powder cohort. Those subjects who opt to initiate treatment with oral powder and subsequently switch to tablets following completion of the powder intensive PK visit, or those subjects who are required to change dose strengths of the tablet based on the weight-based dosing requirements, will also have the option to participate in a second tablet intensive PK visit.

Irrespective of choice of formulation (tablet versus oral powder), if a subject is switching from tablets to powder, the subject must be taking powder for at least 2 weeks prior to the oral powder intensive PK visit. Similarly, subjects must be taking tablets for at least 2 weeks prior to the tablet intensive PK visit.

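### The two-week run-in before an intensive PK visit counts time on the formulation, not on the current strength, so a child can qualify within days of a tablet-strength change

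*Protocol*

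**What the plan says.** Protocol Section 6.6 offers a second tablet intensive PK visit to two groups. One is children who start on powder and move to tablets. The other is "those subjects who are required to change dose strengths of the tablet based on the weight-based dosing requirement".

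The run-in sentence that follows is addressed to "Subjects initially treated with tablets or subjects switching from oral powder to tablet", who "must be receiving tablets for at least two weeks prior to the tablet intensive PK visit". It does not mention strength. The synopsis has the same rule ("subjects must be taking tablets for at least 2 weeks prior to the tablet intensive PK visit"), and so does SAP Section 1.2 ("subjects must be taking tablets for at least 2 weeks prior to the" tablet PK visit). The powder rule in Section 6.6 is built the same way: "the subject must be taking the oral powder for at least 2 weeks prior to the intensive PK visit", with no reference to the number of scoops.

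The second visit is placed by calendar, "with the second intensive PK substudy occurring after the Week 12, but prior to the end of the double-blind phase", with no minimum interval from a strength change. The tablet cohort has an accrual target of 12 subjects at each of 150, 200, 250 and 300 mg, placebo included. Samples are taken pre-dose and at 1, 2, 4 and 8 h. Section 8.10 lists Ctau, AUCtau and CL/F among the parameters to be summarised.

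**The concern.** A stabilisation period before intensive sampling makes sense only if it ensures that the profile reflects the dose it is attributed to. The plan sets that period at two weeks but applies it to the formulation. For children who change strength, a group the plan expressly invites back, the rule does nothing: a child moving from 150 to 200 mg has been on tablets throughout and meets it immediately.

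On the first new dose, the pre-dose sample comes entirely from the old strength, and so does part of the area under the curve. If that profile is read as exposure at the new strength, exposure looks too low and CL/F too high. PK is a secondary objective and tablet accrual is organised by dosage level, so a small number of such profiles could blur the comparison the cohort was set up to allow.

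**Working it through.** The documents state no PK sample-size or precision figure, so there is nothing to reproduce. The check has two parts.

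**1. Does any other rule close the gap?**

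- Section 6.7 requires morning dosing for at least 10 days and an overnight fast. This concerns time of day and food only.
- Section 6.9 requires a dosing diary for at least 10 days before the PK visit. It does not mention strength. All children also complete diaries in the 10 days before Weeks 8 and 32. Section 6.2.1 has weight measured and drug dispensed at those visits, so a strength change and a PK visit can fall together with the diary requirement met.
- Section 6.6 lists what is recorded at each PK draw: time of last dose, food, and time of draw. Neither strength nor date of last change is on that list. Dispensing dates are kept under Section 5.5.

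No rule in the protocol or SAP requires time on the current strength.

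**2. How large is the effect?**

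Assumptions: linear one-compartment kinetics, dosing every 24 h, old strength at steady state before the change. The documents give no plasma tenofovir half-life, so I assume a range of 6 to 24 h.

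- Carry-over per interval: r = exp(−ln 2 × 24 / half-life). This gives 0.0625 (6 h), 0.25 (12 h), 0.397 (18 h) and 0.50 (24 h).
- Pre-dose value at the m-th new dose, relative to the new steady state: 1 − (1 − old/new) × r^(m−1).
- AUCtau in the m-th interval, relative to the new steady state: 1 − (1 − old/new) × r^m.

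First new dose (m = 1):

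| Change (mg) | Pre-dose | AUCtau, 6 h | 12 h | 18 h | 24 h |
|---|---|---|---|---|---|
| 150 to 200 | 75% | 98.4% | 93.8% | 90.1% | 87.5% |
| 200 to 250 | 80% | 98.8% | 95.0% | 92.1% | 90.0% |
| 250 to 300 | 83% | 99.0% | 95.8% | 93.4% | 91.7% |

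The pre-dose shortfall of 17% to 25% does not depend on the half-life. Adding first-order absorption (1.0/h) to the worst case, 150 to 200 mg at 24 h, lowers AUCtau from 87.5% to 87.1%. The AUCtau shortfall is therefore about 1% to 13%. CL/F is dose divided by AUCtau, so it is high by 1/0.99 − 1 = 1% up to 1/0.871 − 1 = 15%.

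Seventh new dose, worst case (150 to 200 mg, 24 h): pre-dose shortfall 0.25 × 0.5^6 = 0.4%; AUCtau shortfall 0.25 × 0.5^7 = 0.2%.

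**Effect on a dose-level mean.** Twelve subjects at 2:1 give about 12 × 2/3 = 8 active profiles per level. One first-dose profile among eight moves the mean AUCtau by at most about 13%/8 = 1.6%, and the mean pre-dose value by at most 25%/8 = 3.1%.

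**Half-life outside the range.** The only half-life in the documents is 95 h (Section 1.2.2.1). It is for the active anabolite in hepatocytes, not plasma tenofovir. Even at 95 h, fourteen days on the new strength brings a 150 to 200 mg change to about 98% of the new steady state.

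**The case against.** The strongest reply is practical. Weight is measured and drug dispensed at scheduled visits, so the natural order is strength change, then ten days of diary, then the PK visit. After ten days on 200 mg with a 24 h half-life, the pre-dose error is 0.25 × 0.5^10, about 0.02%. This stands as a reason to expect few affected profiles. It is not a bar, because the diary rule is silent on strength and a card can be completed on the old one.

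The second reply is that the relevant detail may lie elsewhere. Section 6.6 refers to a PK manual and SAP Section 1 to a separate PK SAP. Neither was supplied, and either could contain a same-strength rule or criteria for setting profiles aside. This also stands.

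A reader might go further and infer that the plan will publish biased exposure by dose level. The documents do not support that. Section 8.10 says only that parameters will be listed and summarised. Summaries by strength are an inference from the per-level accrual target. Nor do the documents say that the pre-dose sample stands in for the 24 h value. Sampling stops at 8 h, but λz is a listed parameter, so extrapolation is equally possible. How the error divides between Ctau and AUCtau depends on that choice.

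The powder case is weaker still. The wording gap is the same, but the powder cohort has no accrual by dose and no second powder visit is offered for a change in scoops.

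**Conclusion.** The wording gap is real and appears in the protocol body, the synopsis and the SAP. The run-in is defined by formulation, so a child whose tablet strength has just changed can be sampled before reaching steady state on it. The diary rule makes this uncommon without excluding it.

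The size is modest: on a first new dose, a pre-dose value 17% to 25% low and AUCtau about 1% to 13% low, falling to 0.4% or less by the seventh dose. The AUCtau and seventh-dose figures rest on linear kinetics and an assumed plasma half-life of 6 to 24 h. The pre-dose figure needs only linearity and prior steady state. Only active-arm strength changers sampled within days of the change are affected, and the documents do not allow a count of them. The primary efficacy endpoint is untouched. This is a cheap improvement to a secondary objective, not a defect that threatens the trial.

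**What to change.** In Protocol Section 6.6, the synopsis and SAP Section 1.2, state the run-in as at least two weeks on the current formulation at the current tablet strength, or the current number of scoops for powder. This governs when PK samples are taken and leaves dosing as it is.

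SAP Section 1.3 reports that enrolment closed at 90 randomised, and PK visits must precede the end of blinded treatment, so rewording will come too late for many or all of them. For visits already done, use the dispensing dates to flag profiles that miss the rule. Keep them in the listings and repeat any dose-level PK summary without them. Flagging with a sensitivity summary is preferable to automatic exclusion when a level holds about eight active children. If the PK SAP or PK manual already contains the rule, a cross-reference is sufficient.

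The cost is small: one phrase in three places, a date check per profile, and possibly a few flagged profiles. A second visit may have to move by up to two weeks, and a child whose strength changes in the last two weeks of blinded treatment could not have one.
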